Hypothesis 1: Veterans in TrIGR, compared to Veterans in SCT, will have significantly greater reductions in deployment-related guilt severity (TRGI) at the end of treatment and follow-up period. This hypothesis will be tested using Mixed Effects models. We will examine two specific forms of the Mixed effects model strategy; random regression models (RRM), also known as hierarchical models (HLM), Linear Mixed Effects models (LMEs) or multilevel models; and mixed model analysis of variance (MMANOVA). The Hierarchical Linear Model assumes that change over time is linear while MMANOVA considers time as a categorical classification variable and does not assume any specific profile between the outcome variable and time. Each outcome variable will be graphed versus time for each subject to evaluate what function of time bests describes the data. If the change is linear we will precede with the LMEs structure. If the time pattern is not immediately apparent we will proceed with the MMANOVA. This method allows the inclusion of subjects with missing data or those who were terminated early in the study, without relying on data imputation procedures. A fully saturated treatment by time model will be utilized for inference. Co-variance structure will be chosen based on Akaike's Information Criterion (AIC). Random group level treatment effects will also be evaluated for importance based on the model AIC. Denominator degrees of freedom will be calculated using the Kenward-Roger small sample correction.

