Data will be analyzed from all randomized subjects on whom we have a baseline assessment and at least one post-baseline evaluation. Responses at baseline through 6 months follow-up will be nested within subjects. Slope (change in outcome over time) will be entered into the model as a random factor and interacted with treatment group. Intercept and slope will be modeled as random effects nested within subject, and treatment group will be a fixed effect. If it is needed based on analyses in stage one, baseline covariates (e.g., demographics) will also be entered as fixed effects. Site and the Treatment by Site interaction will be included as “nuisance parameters;” that is, they must be included to account for possible overall site effects (Site) or possible site differences in treatment effects (Treatments X Site). With the balanced design (equal numbers at each site in each group), ignoring these would not increase the probability of Type I error, but it would increase the Error Sum of Squares, thus increasing the probability of Type II Error. The main effect of treatment represents the common effect size across sites if there is one, or the average site effect, if there is heterogeneity across sites. This is true because sample sizes will be balanced across treatment groups and sites. In any case, the analysis procedures will include site and site interaction effects to avoid allowing site effects to bias treatment comparisons. However, if we detect any imbalances between the treatment groups within each site, we will follow the primary analyses above with subsequent analyses considering the imbalances to verify that the conclusions are not affected by the imbalances.

Hypothesis 2: Veterans in TrIGR, compared to Veterans in SCT, will have significantly greater reduction in distress (BSI-18), shame (ISS), and significantly more improved in their quality of life (WHO-QOL-BREF) at the end of treatment and at follow up periods. This hypothesis will be analyzed using a method similar to that for testing hypothesis 1.

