Power analysis. Overall, assumptions for our sample size estimation were: (1) sufficient power to test different hypotheses using different analytical models; (2) the reality of recruiting subjects and conducting the study; (3) project cost considerations; and (4) study duration. Therefore, for hypotheses 1 and 2, we performed our calculations using several different methods, each with varying levels of complexity and selected a sample size that provided us with a minimum of 80% power for medium to large effect sizes in each case. The medium effect size was chosen based on the findings reported above. First, we estimated the power using an analysis of variance (ANOVA) in which the person-specific regression coefficient can be used as the dependent variable. Second, we used the method provided by Hedeker and colleagues for the Random Regression Model [80] and finally, we used the RMASS program provided by Hedeker (<http://tigger.uic.edu/~hedeker/ml.html>). Overall, we believe that the proposed sample size of 150 subjects would provide us with minimum of 90% power to detect the medium effect size for hypothesis 1 and 80% for hypothesis 2. Note: Medium effect size is defined as a between-group difference increasing linearly from 0 at baseline to .5 SD units at the last time point. The minimum power estimation is based on sample size calculation for 10% to 20% attrition, correlations of 0.2, 0.5, and 0.8 between the repeated measures, and for medium and large effect sizes. For hypothesis 3, we used the procedures defined by [89] for estimating sample sizes needed to achieve 80% power to detect the mediated effect. They defined regression coefficients of .14, .39, and .59 to be small, medium, and large, respectively. For mediation analysis, we also assume a medium effect based on finding reported above. Using the Sobel test procedure, we estimated that with the proposed sample we will achieve 80% power to detect a mediated effect.

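### The stated minimum power of 90% (hypothesis 1) and 80% (hypothesis 2) is not reached over the stated correlations with four assessments and the planned slope model

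*Combined protocol and SAP*

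**What the plan says.** The power paragraph closes section 9.11.2. Its claim for the primary hypothesis reads: "proposed sample size of 150 subjects would provide us with minimum of 90% power to detect the medium effect size for hypothesis 1". The corresponding figure for hypothesis 2 is 80%. The minimum is "based on sample size calculation for 10% to 20% attrition, correlations of 0.2, 0.5, and 0.8 between the repeated measures", for medium and large effects. A medium effect is a "between-group difference increasing linearly from 0 at baseline to .5 SD units at the last time point".

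Three methods are named. The first is an "analysis of variance (ANOVA) in which the person-specific regression coefficient can be used as the dependent variable"; the others are a published random-regression method and a power program. The authors say they "selected a sample size that provided us with a minimum of 80% power for medium to large effect sizes in each case".

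The paragraph does not give the number or spacing of waves, the covariance structure, the handling of baseline, the dropout pattern or the alpha.

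Other sections bear on the claim:

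- Section 9.3 schedules four assessments: baseline, post-treatment, 3 months and 6 months. Sections 9.1 and 9.3 add weekly self-reports during treatment.
- Section 9.11.2 enters treatment group as a fixed effect and adds: "Slope (change in outcome over time) will be entered into the model as a random factor and interacted with treatment group". The baseline group difference is therefore estimated, not set to zero.
- The same section also says: "A fully saturated treatment by time model will be utilized for inference".
- Section 9.11.1 sets two-sided tests at 0.05 with a Bonferroni correction within each hypothesis. Section 9.11.2 names three outcomes for hypothesis 2 (distress, shame, quality of life).

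**The concern.** A between-group difference that reaches only 0.5 SD at the last visit is hard to detect when repeated measures correlate weakly, because a low correlation inflates the variance of within-person change. It was therefore doubtful that 150 participants could give at least 90% power at a correlation of 0.2 with 20% attrition.

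The stake is how a null result will be read. The paragraph tells readers that the type II error for hypothesis 1 is at most 10% over the whole stated range, and for hypothesis 2 at most 20%. If the true figures are much higher at plausible correlations, a null result would be taken as stronger evidence against benefit than it is.

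**Working it through.** **Inputs from the documents.** N = 150 (9.1), equal allocation (9.5.2), so 75 per arm; final difference 0.5 SD, linear from zero; correlations ρ = 0.2, 0.5, 0.8; attrition 10-20%; two-sided 0.05 for hypothesis 1 (critical value 1.960). For hypothesis 2, 0.05/3 = 0.0167 (critical value 2.394).

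**Assumptions.** Compound symmetry, total SD 1, no random-slope variance, normal approximation. Calendar spacing takes a six-week treatment: 0, 1.5, 4.5 and 7.5 months.

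**Step 1: the plan's first method, by hand.** With four equally spaced visits (0, 1, 2, 3), Sxx = 5 and the slope difference is 0.5/3. A person's slope has variance (1 − ρ)/5, so

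z = (0.5/3) × √(5n / (2(1 − ρ))), power = Φ(z − critical value).

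| n per arm | ρ | z | Power at 0.05 | Power at 0.0167 |
|---|---|---|---|---|
| 75 (no attrition) | 0.2 | 2.55 | 72.3% | 56.3% |
| 75 | 0.5 | 3.23 | 89.8% | 79.8% |
| 67.5 (10% lost) | 0.2 | 2.42 | 67.7% | 51.1% |
| 67.5 | 0.5 | 3.06 | 86.5% | 74.8% |
| 67.5 | 0.8 | 4.84 | 99.8% | 99.3% |
| 60 (20% lost) | 0.2 | 2.28 | 62.6% | 45.5% |
| 60 | 0.5 | 2.89 | 82.3% | 68.9% |
| 60 | 0.8 | 4.56 | 99.5% | 98.5% |

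The row for ρ = 0.5 without attrition (89.8% / 79.8%) resembles the stated pair. It lies outside the stated attrition range and is not the minimum over the correlations. At ρ = 0.2 even full retention gives only 72.3%, so attrition is not the main cause.

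**Step 2: the slope model with partial data kept.** Generalised least squares with intercept, time, group and group × time. Ranges cover 10-20% attrition and four dropout patterns (early, gradual, late, completers only).

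| Four visits | ρ = 0.2 | ρ = 0.5 | ρ = 0.8 |
|---|---|---|---|
| H1, equal spacing | 62.6-70.0% | 82.3-88.0% | 99.5-99.9% |
| H1, calendar spacing | 65.2-72.2% | 84.5-89.6% | 99.7-99.9% |
| H2 at 0.0167, both spacings | 45.5-56.2% | 68.9-79.5% | 98.5-99.6% |

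Hypothesis 2 misses 80% at ρ = 0.2 even at alpha 0.05, since it then has the power of hypothesis 1. Hypothesis 1 reaches 90% only once ρ is about 0.53-0.60 (equal spacing) or 0.51-0.58 (calendar).

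**Step 3: the saturated model.** Hypothesis 1, at ρ = 0.2 / 0.5 / 0.8: the 3-df treatment-by-time test has 46-56 / 67-78 / 98-99.5%; the 6-month change contrast has 58-65 / 78-84 / over 99%. With baseline means constrained equal, ρ = 0.2 still gives only 73-83% (3 df) and 80-84% (6-month contrast).

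**Step 4: inputs that come close to the stated pair at ρ = 0.2.** Ten waves means the four assessments plus six weekly scores; on calendar spacing they were placed at 0, weekly from 0.25 to 1.5, then 1.75, 4.75 and 7.75 months.

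| Slope model, ρ = 0.2 | H1 / H2, 20% gradual | H1 range | H2 range |
|---|---|---|---|
| Ten waves, equally spaced | 89.7% / 79.7% | 87-93% | 76-85% |
| Ten waves, calendar | 83.3% / 70.2% | 82-88% | 69-76% |
| Four visits, equal, baseline constrained | 89.4% / 79.2% | 88-93% | 77-85% |
| Four visits, calendar, baseline constrained | 87.2% / 75.9% | 86-91% | 74-82% |
| Ten waves, equal, baseline constrained | 98.6% / 96.0% | 98-99% | 95-98% |
| Ten waves, calendar, baseline constrained | 89.0% / 78.6% | 89-93% | 78-85% |

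**Step 5: direction of the covariance assumption.** Under AR(1) with the same adjacent correlations and four equally spaced visits, hypothesis 1 falls to 51-58 / 55-62 / 79-86%. Adding random-slope variance of 0.25 SD² at the last visit to the compound-symmetry model (equal spacing, 20% gradual attrition) gives 59.3 / 75.2 / 95.1%. The main assumptions therefore favour the plan.

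**The case against.** The strongest reply is that this is a reporting gap and not a proven arithmetic error. The paragraph fixes neither four waves nor a free baseline difference. Weekly measures are planned, and section 9.11.2 nests all responses from baseline to 6 months without limiting them to four visits. The contents of Table 3, which could show what is collected weekly, are not in the text available. With late dropout at 20% and ρ = 0.2, ten equally spaced waves give 91.9% / 83.3%, and four equally spaced visits with a constrained baseline give 90.9% / 81.6%; both meet the claim. At ρ = 0.5 the single rescues also clear it: their worst cells run from 91.9% to 97.4% for hypothesis 1 and from 83.3% to 93.5% for hypothesis 2. The lowest figures above come from completers-only cells, whereas the mixed model keeps partial data. Without those cells the equal-spacing minima rise from 62.6% to 66.0% at ρ = 0.2 and from 82.3% to 84.0% at 0.5.

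Much of this stands. The sponsor's arithmetic may be right for inputs it did not print, and the shortfall at 0.5 needs both four waves and an unconstrained baseline.

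It does not rescue the claim as written. Equal spacing of ten waves treats one-week and three-month gaps as the same; on calendar spacing the planned slope model stays at 82-88% at ρ = 0.2. Constraining the baseline departs from the group fixed effect in section 9.11.2. The saturated model is lower still. Dropping completers-only cells leaves ρ = 0.2 more than 20 points short of 90%.

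**Conclusion.** The concern holds. For the four scheduled assessments and the slope model of section 9.11.2, the stated minimum fails at two of the three correlations for hypothesis 1, and also at two of three for hypothesis 2 at its Bonferroni alpha. The implied type II error for hypothesis 1 is about 28-37% at ρ = 0.2 and 10-18% at 0.5, against a stated maximum of 10%. For hypothesis 2 at 0.0167 it is about 44-54% and 20-31%, against 20%.

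These figures rest on 75 per arm, compound symmetry, no random-slope variance and an unconstrained baseline difference. They show that the claim does not follow from the documented design. They do not show that the sponsor miscalculated from its own unstated inputs. At ρ = 0.8 under compound symmetry both claims are met. The text available does not say which correlation is expected. The point should be fixed; confidence is medium because the missing inputs could move the figures.

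**What to change.** Keep N = 150 and the planned tests. In the power paragraph of section 9.11.2:

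1. Delete the word minimum, or name the correlation and attrition at which 90% and 80% apply.
2. Add a small table of power for the planned treatment-by-time test at correlations 0.2, 0.5 and 0.8 and attrition 10% and 20%, with hypothesis 2 at its Bonferroni alpha.
3. Beside it, state the waves and spacing (including whether weekly scores enter), covariance structure, slope variance, baseline handling, dropout pattern and alpha, and label the figures as conditional on these.
4. If weekly scores or a baseline constraint were used, say so and make the analysis model in section 9.11.2 match.

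The cost is some wording and one table, with no extra participants. The drawback is that the stated power becomes less favourable unless the favourable inputs were in fact used.

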Hypothesis 3: Per the NAG model, guilt cognitions (TRGI Cognitions Scale), distress (BSI-18) and avoidant coping (COPE) will partially mediate the treatment effect on guilt severity (TRGI). For this hypothesis, we will use the same mixed effect model procedure identified in hypothesis 1. We will utilize the analytic strategy described by [85] [86] to test the mediation effect. Based on this strategy, four conditions must be met: (1) a significant relationship between the independent variable (i.e., intervention

condition) and the dependent variable, (2) a significant relationship between the independent variable and the proposed mediator, (3) a significant relationship between the mediator and the outcome, and (4) the relationship between the independent variable (intervention) and outcome must be significantly lower after controlling for the proposed mediator. To test for significant mediation, we will conduct a Sobel test. We will also use the formula provided by [87] to determine the percentage of the intervention condition to primary outcome path that was accounted for by change in our mediator [88].

Exploratory Analyses. The first exploratory objective, whether TrIGR, as compared to SCT, is associated with greater decreases in PTSD and depression symptom severity, greater reductions in suicidal ideation (SI) and greater reductions in alcohol/substance use, will be explored using mixed effect method as explained for hypothesis 1. The second and third objectives—whether reductions in guilt, shame, and avoidant coping will partially mediate the treatment effect on PTSD symptoms among Veterans with a PTSD diagnosis and among Veterans with a depressive disorder—will be explore using analytic strategy as described for hypothesis 3 [85].

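### Hypothesis 3: the stated 80% power is for the Sobel test alone, not the four-condition rule that decides mediation, and the Sobel step gives away power

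*Combined protocol and SAP*

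**What the plan says.** Hypothesis 3 names three mediators of the treatment effect on guilt severity: guilt cognitions, distress and avoidant coping. Section 9.11.2 sets the decision rule: "Based on this strategy, four conditions must be met". They are (1) a significant treatment effect on the outcome, (2) a significant treatment effect on the mediator, (3) "a significant relationship between the mediator and the outcome", and (4) that the treatment–outcome relationship "must be significantly lower after controlling for the proposed mediator". It then adds: "To test for significant mediation, we will conduct a Sobel test". The exploratory PTSD and depression mediation analyses "will be explore using analytic strategy as described for hypothesis 3".

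The power paragraph of the same section gives the sample that "would provide us with minimum of 90% power to detect the medium effect size for hypothesis 1 and 80% for hypothesis 2". For Hypothesis 3 it says: "Using the Sobel test procedure, we estimated that with the proposed sample we will achieve 80% power to detect a mediated effect". It cites regression coefficients of .14, .39 and .59 as small, medium and large, and assumes a medium effect. For Hypotheses 1 and 2 a medium effect is 0.5 SD at the last time point.

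Section 9.11.1 sets two-sided tests at .05, a Bonferroni correction within each hypothesis, and a level of .01 where applicable. It does not say which of these lies behind the Hypothesis 3 figure.

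**The concern.** The 80% belongs to one component of the rule. The rule also needs condition 1, so its power can equal the Sobel power but never exceed it. No power is given for the rule as a whole, so a negative result on Hypothesis 3 could be read as coming from an 80%-powered test when it did not.

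The Sobel test is also an inefficient last step. Conditions 2 and 3 already test the two paths that make up the indirect effect, and Sobel then demands more of the same two estimates.

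Hypothesis 3 is the plan's formal test of how TrIGR works. It is a secondary aim, so the primary conclusion is not at stake.

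**Working it through.** **Inputs from the plan.** N = 150 (9.1); up to 20% loss (9.5.4), so 150 × 0.8 = 120; three mediators, so .05/3 = .0167; medium path .39; medium group difference 0.5 SD; 90% power for Hypothesis 1. N = 120 is a pessimistic bound, because 9.11.2 analyses anyone with a baseline and one later evaluation.

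**Assumptions, because the plan gives no value.** b = .39; direct effect and treatment coding as stated below; condition 1 tested at .05; condition 4 taken as the Sobel test, since in a linear model the drop in the treatment coefficient equals a × b. The model is single-wave least squares with unit residual SDs, 40,000 simulated trials per setting unless noted.

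**1. The plan's 80%.** Sobel power with a = b = .39, N = 150 and .05 is 98–99% for unit-variance treatment and 57% for a 0/1 arm. Two input sets return about 80%:
- A: treatment shifts the mediator 0.5 SD, N = 150, .05: 79–80%.
- B: a = .39 with treatment coded −1/+1 (unit variance), N = 120, .05/3: 81–82%.

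They differ in substance. On −1/+1 coding the arms are two units apart, so a = .39 means 2 × .39 = 0.78 SD. Section 8 lists the same three mediators under Hypothesis 2, where the plan's medium effect is 0.5 SD.

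**2. The written rule.** The within-arm outcome SD is √(1 + .39²) = 1.073. A total effect of 0.5 SD needs a direct effect of .342 in A, (.342 + .5 × .39)/1.073 = 0.50, and .116 in B, 2 × (.116 + .39 × .39)/1.073 = 0.50. Condition 1 then passes 77% of the time at N = 120 and 86% at N = 150. The second figure in each pair below raises the direct effect until condition 1 passes 90%, as claimed for Hypothesis 1 (total effect 0.597 SD at N = 120, 0.532 SD at N = 150).

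| Setting | Sobel alone | Written rule | Conditions 1–3 without Sobel |
|---|---|---|---|
| A, N=150, .05 (reproduces 80%) | 79.6% | 70.7 / 73.3% | 75.5 / 78.4% |
| B, N=120, .05/3 (reproduces 80%) | 81.5% | 65.0 / 74.5% | 72.5 / 83.9% |
| A, N=120, .05/3 | 38.1% | 32.9 / 36.2% | 50.1 / 56.0% |
| A, N=150, .05/3 | 56.1% | 51.0 / 52.6% | 65.3 / 67.6% |
| B, N=150, .05/3 | 93.5% | 81.0 / 84.5% | 84.1 / 87.9% |

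At .01, N = 120, with condition 1 at 90%, the written rule has 25.8% (A) and 66.1% (B); conditions 1–3 alone have 48.5% and 81.1%.

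**3. Direct effect varied.** For B at .05/3 the written rule has 71% (N = 120) and 86% (N = 150) with a direct effect of .14, and 82% and 94% with .39. The last is a total effect of 2 × (.39 + .152)/1.073 ≈ 1 SD, and there the rule equals Sobel. With no direct effect, condition 1 dominates: 18% for A (N = 150, .05) and 29% for B's inputs with a standardised treatment variable. Dropping Sobel then gives only 19% and 32%.

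**4. Why Sobel loses power.** From z = ab/√(a²s_b² + b²s_a²),

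1/z² = s_a²/a² + s_b²/b² = 1/z_a² + 1/z_b².

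So |z| is below both |z_a| and |z_b|, whatever the coding, direct effect or N. With equal paths, z = z_a/√2. At .05/3 each path must reach √2 × 2.394 = 3.386 (p = .0007), where testing both paths needs 2.394. At .05 each must reach 2.772 (p = .0056). Apart from the small gap between t and normal cut-offs, conditions 2 and 3 hold whenever Sobel passes; where this was counted, no simulated trial passed Sobel and failed the joint test.

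**5. Type I error** (N = 120, nominal 1.67%, condition 1 kept). Removing Sobel moves it from 0.3% to 1.1% with a = 0, b = .39, and from 0.1% to 0.8% with a = 0.5 SD, b = 0. Without condition 1 the highest joint-test value was 1.74% (simulation SE 0.06), consistent with nominal.

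**6. Alternatives** (condition 1 kept). A percentile bootstrap at .05/3 (1,500 trials) gives 51/58% (A) and 73/85% (B) at N = 120, much as the joint test. With three mediators (residual correlation .5 assumed, 20,000 trials, N = 120, condition 1 at 90%), Holm instead of Bonferroni lifts the joint test from 56% to 64% (A) and from 84% to 87% (B) per mediator.

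**The case against.** The plainest reading of the power paragraph is a = b = .39 with the full 150 at .05. With unit-variance coding, Sobel power is then about 99%, the written rule has about 85% with a 0.5 SD total effect and 89% with condition 1 at 90%, and dropping Sobel gains under one point. The 80% could be a target that was met and not a point estimate. This stands as a setting without shortfall, but it does not return the stated figure, and the same coefficients with 0/1 coding give 57%. The plan does not say which applies.

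The lowest figures (33–36%) come from a setting where Sobel itself has 38%, so they do not show what happens when the 80% is right. That is true. They show what follows if the mediators move by the plan's own medium effect and its Bonferroni rule is applied.

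Condition 1 is essentially Hypothesis 1, whose power is stated separately, and a failure there would be visible. When the direct effect is small it is the main source of loss and replacing Sobel recovers little. Both points stand, though Hypothesis 3 posits partial mediation, so no direct effect is an edge case.

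Sobel is valid, only conservative, and the planned analysis is a repeated-measures mixed model, not single-wave regression. The percentages are therefore approximate. The ordering of the rules does not rest on them.

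**Conclusion.** The concern holds. The 80% is tied to the Sobel procedure and is at best an upper limit for the four-condition rule; this follows from the text and depends on no assumed input. That Sobel can only subtract from conditions 2 and 3 follows from the identity.

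The size of the shortfall is uncertain because the plan omits the inputs. Where the 80% reproduces, the rule has about 65–75% (B) or 71–73% (A) for a total effect between 0.5 SD and the size that gives condition 1 90% power. It is lower with a smaller direct effect, and there is no shortfall when the total effect is about 1 SD. Replacing Sobel gains about 5 to 9 points in those two settings, 14 to 20 points with a 0.5 SD mediator shift at .05/3, and almost nothing where Sobel power is already near 99%. The stated figure is not shown to be wrong for Sobel. The change should be made, but it concerns a secondary hypothesis and leaves the primary conclusion untouched.

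**What to change.** 1. Decide each mediator by joint significance of the treatment–mediator path (condition 2) and the mediator–outcome path, stated explicitly as adjusted for treatment (condition 3). Remove condition 4 and the Sobel test as decision criteria. A percentile-bootstrap interval for a × b, resampling participants, is an acceptable alternative criterion and should be reported in either case, because joint significance gives no interval. Apply Bonferroni or Holm over the three mediators.
2. State one significance level for Hypothesis 3: say whether .05/3 or .01 applies to the mediators, and test condition 1 at .05 as in Hypothesis 1.
3. Restate the power for the rule adopted, giving a, b, direct effect, treatment coding, significance level and analysed N, and reconcile a with the 0.5 SD used for Hypothesis 2. Accept that the result may be below 80%.
4. Optionally, drop condition 1. At .05/3 the joint test alone has 60% (A) and 93% (B) at N = 120, and 73% and 98% at N = 150. Mediation could then be declared without a significant treatment effect, which is broader than the hypothesis as worded.

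The cost is SAP wording and a few lines of code, with no new visits or data. Type I error rises from well below nominal towards nominal, and cannot exceed it if the path tests are valid. The exploratory mediation analyses, which borrow this strategy, should follow the same change.
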